7. ARCHIVING

Archiving of this project will follow the sponsors (NBT) guidelines, as outlined in SOP RI/QMS/SOP/010

8. Safety Reporting

Serious and other adverse events will be recorded and reported in accordance with the International Conference for Harmonisation of Good Clinical Practice (ICH GCP) guidelines, MEDDEV guidance on medical devices and the Sponsor's Research related adverse event reporting policy.

8.1 Definitions

Investigational Medical Device: Medical device being assessed for safety or performance in a clinical investigation

Adverse Event: Any untoward medical occurrence, unintended disease or injury or any untoward clinical signs (including an abnormal laboratory finding) in subjects, users or other persons whether or not related to the investigational medical device.

A serious adverse event (SAE): Any serious untoward clinical occurrence as a result of a trial related procedure, that:

- Results in death
- Is life threatening – defined as an event in which the subject was at risk of death during the time of the event
- Requires hospitalisation or prolongation of existing hospital admission
- Results in persistent or significant disability or incapacity

Device deficiency: Inadequacy of an investigational medical device related to its identity, quality, durability, reliability, safety or performance. This may include malfunctions, use error, or inadequacy in the information supplied by the manufacturer.

Adverse Device Effect (ADE): Adverse event related to the use of an investigational medical device.

Serious Adverse Device Effect (SADE): Adverse device effect that has resulted in any of the consequences characteristic of a serious adverse event.

Unanticipated Serious Adverse Device Effect (USADE): Serious adverse device effect which by its nature, incidence, severity or outcome has not been identified in the current version of the risk analysis report.

Clinical judgement should be exercised in deciding whether an adverse event/reaction should be classified as serious in other situations. Important adverse events/reactions that are not immediately life-threatening or do not result in death or hospitalisation, but may jeopardise the subject or may require intervention to prevent one of the other outcomes listed in the definition above, should also be considered serious.

8.2 Expected AEs, SAEs, ADEs, and SADEs

8.2.1 Expected AEs

- Parent or child dropping or otherwise breaking the Language Explorer device
- Injury received due to the breakage of the language explorer device

- Child withdraws assent to participation in the assessment

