4) SLT and Parent Interviews

An interview schedule will be used to guide qualitative data collection from SLTs and parents/carers, (Appendix O 'Interview Schedule (SLT)' and Appendix P 'Interview Schedule (Parent)').

4.3 PROCEDURES FOR DATA COLLECTION:

The procedures for collecting the data vary for each data type and will be described here:

1) *The Language Explorer*

Each clinical site will collect data from 20 children. Two protocols for collection of Language Explorer data are provided: one for remote facilitation for children aged 6 years 0 months to 7 years 11 months and one for when the app is used in person in the clinical setting for children aged 4 years 0 months to 5 years 11 months.

Remote (ages 6 years 0 months to 7 years 11 months):

Parents will be contacted in advance of the remote appointment by the local SLT and asked to download the Language Explorer app to a compatible device. Wherever possible this will be on a tablet, but if that is not available, the child could be assessed on a mobile phone. At the agreed time for the remote assessment, the SLT will take assent from the child and confirm eligibility and confirm consent as outlined in the consent forms. S/he will then ask the parent facilitating the session to open the Language Explorer app. The SLT will ask the parent to use the child's unique study ID number as their username for the tool. This will ensure that the data can be retrieved by the developers and provided to the local SLT and to the study team at BSLTRU. The parent will then be asked to use the Language Explorer app to collect a language sample from the child using the usual processes involved in the tool (i.e. child hears a story and retells it and then completes comprehension and sentence repetition tasks as described above). The app will record the child's speech as they respond to the stimuli and questions on the tool. For the data to be useful and the child's data to be included in the analysis, the story retell task must be completed as a minimum. The app will use this recording to generate an automated transcription. See Appendix N 'Language Explorer Screen shots' for images taken from the app.

During this, the SLT will observe the process. This is important to facilitate transcription of the recorded sample and for the process of being interviewed by the study team later.

In person in a clinical setting (to include NHS clinics, schools, early years settings) (ages 4 years 0 months to 5 years 11 months):

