8.2.3 Expected ADEs

-Instructions not clear and users not able to access or use the device.

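### The expected-event lists in section 8.2 do not follow the definitions in section 8.1: the only expected ADE is a device deficiency, and two of the three expected AEs are not adverse events

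*Protocol*

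**What the plan says.** Protocol section 8.1 sets up three classes that matter here.

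- An AE is "Any untoward medical occurrence, unintended disease or injury or any untoward clinical signs (including an abnormal laboratory finding) in subjects, users or other persons", and it counts "whether or not related to the investigational medical device".
- An ADE is an "Adverse event related to the use of an investigational medical device".
- A device deficiency is an inadequacy of the device itself. Of this class the protocol says: "This may include malfunctions, use error, or inadequacy in the information supplied by the manufacturer".

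Section 8.2 then lists what is expected.

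- Section 8.2.1 (AEs) has three entries: "Parent or child dropping or otherwise breaking the Language Explorer device"; "Injury received due to the breakage of the language explorer device"; and the child withdrawing assent.
- Section 8.2.3 (ADEs) has one entry: "Instructions not clear and users not able to access or use the device".
- Sections 8.2.2 and 8.2.4 expect no serious events of either kind.
- There is no list for device deficiencies.

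The surrounding text gives the device label some weight. The opening of section 8 commits the study to MEDDEV device guidance. Section 9.1 says that MHRA approval will be sought. Section 9.5 divides responsibility between the co-sponsors: the NHS trust monitors safety in so far as it concerns study conduct and not the device, and the developer answers for the device.

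**The concern.** The lists in 8.2 are the only worked examples that site staff have of how the 8.1 definitions apply, and on several items the two sections disagree. The clearest case is the sole expected ADE, which describes a usability or information problem and no harm to a person.

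What is at stake is consistent classification. A therapist who follows 8.2 would label a failed log-in or a confusing instruction an adverse device effect. A therapist who follows 8.1 would label the same event a device deficiency. Such events are easy to foresee: under section 4.3, children aged 6;0 to 7;11 are assessed remotely, on a device found by the family and with a parent operating the app. Because section 9.5 divides oversight by whether a matter concerns the device, the label also bears on which co-sponsor deals with the event.

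**Working it through.** The protocol states no safety rate, count or threshold, so there is no figure to reproduce. The check applies two questions from section 8.1 to each listed item.

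- (a) Is it a medical occurrence, disease, injury or clinical sign in a person?
- (b) Is it related to use of the investigational device?

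If only (a) holds, the item is an AE. If (a) and (b) both hold, it is an AE and also an ADE. If (a) fails but the item shows an inadequacy of the device, its use or its information, it is a device deficiency.

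| Item | Listed as | (a) | (b) | Class under 8.1 |
|---|---|---|---|---|
| Unclear instructions, or unable to access or use | ADE (8.2.3) | No | Yes | Device deficiency |
| Dropping or breaking, no injury | AE (8.2.1) | No | Depends on hardware | Not an AE; at most a use error or device deficiency |
| Child withdraws assent | AE (8.2.1) | No | Not needed | Not an AE; a participation event |
| Injury from breakage | AE (8.2.1) | Yes | Yes, if hardware is part of the device | AE; also an ADE on that condition |

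**Instructions and access.** An ADE must first be an AE. Someone who cannot follow the instructions or open the app has suffered no medical occurrence, so the item fails at (a). The device-deficiency definition names both use error and inadequate manufacturer information, which is what this item describes. This is a direct contradiction.

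**Breakage.** The list has a separate entry for injury, so the breakage entry covers the event to the hardware alone. That is not an event in a person.

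**Assent.** A child who declines to continue has exercised a choice. Nothing medical is described.

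**Injury.** ADEs are a subset of AEs, so the entry in 8.2.1 is correct as far as it goes. Whether it should also appear in 8.2.3 depends on what the device is. Section 4 describes Language Explorer as an app. In person it runs on supplied iPads; remotely it runs on the family's tablet or phone. Section 8.2.1 nevertheless speaks of a Language Explorer device that can be broken. The protocol does not settle the question.

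**Tally.** Section 8.2.1 has 3 items and 8.2.3 has 1, so 3 + 1 = 4. Of these, 3 do not meet the AE definition. The fourth is correctly placed but may be missing from a second list. Of the expected ADEs, 1 of 1 is not an ADE. Of the items listed as device deficiencies there are 0, although 1 listed item clearly fits that class and another may.

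**Numerical effect.** Section 4.3 says "Each clinical site will collect data from 20 children", so three sites give 3 × 20 = 60 children. The protocol gives no rate for any of these events, so no expected number of misclassified events follows.

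**The case against.** The strongest reply is that these are lists of expected events and not a coding dictionary. The definitions in 8.1 still govern any event that happens, and the lack of a list of expected deficiencies stops nobody from recording one. Section 6 specifies no tabulation of AEs, ADEs or deficiencies. The only reporting trigger in the text of 8.3 is an unexpected serious event, which the AE or ADE label of a non-serious event does not alter. Recording also follows MEDDEV guidance and the sponsor's policy, and the reporting flow chart is not shown. The study is a single language-assessment appointment with no safety objective.

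Much of this stands. It rules out two stronger readings that a reader might draw.

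- *The breakage injury has been filed as not related to the device.* The AE definition covers related and unrelated events alike, so listing the injury there says nothing about relatedness. The entry is at most incomplete, and only if the hardware counts as part of the device.
- *Device-safety counts will be wrong.* The documents do not support this. No count is specified, and sites can still apply 8.1.

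The reply does not rescue the 8.2.3 entry, injury-free breakage or withdrawn assent. The closing paragraph of 8.1 allows clinical judgement, but only on whether an event is serious; it does not widen what counts as an adverse event. The wider text does not fill the gap either: 8.4 provides for collecting adverse events and does not mention device deficiencies, and the text of 8.3 gives no route for non-serious ADEs or for deficiencies.

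**Conclusion.** Section 8.2 is wrong as written against the protocol's own definitions. The sole expected ADE belongs under device deficiency. Two of the three expected AEs are not AEs. The third is correctly an AE and may be missing from the expected ADEs.

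The consequence is limited: events may be classified differently between sites, usability failures may be reported as ADEs, deficiencies may be under-recorded, and events may be routed to the wrong co-sponsor. How often this would happen cannot be computed. None of the study's three objectives is affected.

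The conclusions on instructions, breakage and assent rest only on 8.1 and 8.2. The conclusion on the injury depends on whether the tablet or phone is part of the investigational device. It is a correction the sponsor should make because the contradiction is plain and cheap to remove.

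**What to change.** Reconcile section 8.2 with 8.1.

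1. Add a list of expected device deficiencies and move the instructions and access item into it from 8.2.3.
2. Take injury-free breakage out of the AE list and record it as a use error or device deficiency where that applies.
3. Take withdrawal of assent out of the AE list and record it as a participation event.
4. State whether tablet or phone hardware, whether supplied or family-owned, is part of the investigational device. If it is, list the breakage injury under expected ADEs as well as AEs.
5. Record AEs, ADEs and device deficiencies separately on the event form.

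The cost is a few edited lines in 8.2 and a matching change to the event form. The one visible effect is that device deficiencies will appear as a count of their own.

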8.2.2 Expected SAEs

- No SAEs are expected as a result of the trial.

[figure not shown]
8.2.3 Expected ADEs

-Instructions not clear and users not able to access or use the device.

8.2.4 Expected SADEs

- No SADEs are expected as a result of the trial.

Adverse and serious adverse event reporting flow chart:

8.3 Recording and reporting procedures Any questions concerning adverse event reporting should be directed to the trial manager at BSLTRU in the first instance, who will in turn contact other necessary personnel depending on the nature of the query.

Events that meet criteria for an unexpected SAE should be documented on an SAE form and be reported to the BSLTRU within 24 hours of the event occurring. BSLTRU will forward this to the site PI, study CI and Sponsor. BSLTRU will report suspected unexpected serious adverse reactions (SUSARs) to the REC and copy all reports to the sponsor.

All reported events should be followed to resolution, including those which lead to withdrawal from the trial. The decision to withdraw a patient from the trial due to an adverse event or reaction rests with the local PI. Should a patient request withdrawal, outcome data will still be gathered unless consent for this is also withdrawn.

8.4 Period for recording serious adverse events

Data on adverse events will be collected from recruitment for the duration of the individual's participation in the trial, to the end of their participation, i.e., completion of data collection.

9. REGULATORY ISSUES

9.1 ETHICS APPROVAL

Once Sponsorship approval has been obtained, the Integrated Research Application System (IRAS) will be used to obtain ethical approval and a submission will be made for Health Research Authority (HRA) approval as well. Medicines and Healthcare products Regulatory Agency (MHRA) approval will also be sought.

9.2 CONSENT

Consent forms from clinicians (Appendix D 'Consent Form (Clinicians)') recruited to the study will be collected by the site Service Lead, copied and the originals sent to the study team at BSLTRU.

All consent forms, together with the child participants' assent forms (Appendix J) will be copied and the originals sent to the study team at BSLTRU. On receipt of all consent forms and assent forms at the study base at BSLTRU, they will be scanned and saved to the North Bristol NHS Secure Server. Access will be limited to members of BSLTRU.

An electronic site file will be maintained at each site. All documents will be password protected within a folder on each site's shared drive. The site file will include a subject recruitment log; one each for clinicians, children and parents/carers. The recruitment logs will contain all participants' names and study ID numbers. Limited information from the recruitment log will be sent to the study team at BSLTRU using a password protected document containing the ID numbers for all recruited SLTs, children and parents/carers.

The electronic site file will also include a delegate log to indicate which individuals are GCP trained and have also received training from the study team at the site initiation visit. The site initiation visit will cover the process of ensuring eligibility prior to identification, ensuring consent from completed consent forms and taking assent from children as well as how to carry out the Language Explorer assessment with child participants following the study protocol.

9.3 CONFIDENTIALITY

All data will be kept confidentially and pseudonymised using unique study ID number for all participants. The full identity of each study ID number will be known only to the local site team and the study team at BSLTRU. The document held at each clinical site and the study site linking the study ID with the child's identifying information will be kept securely and confidentially. Each clinical site will only have study ID information for those children recruited at their site.

Clinicians, parents and children who consent to participate in the study will be allocated a study ID number on receipt of the completed consent form. The clinicians will be informed of their own study ID code so that they can use this on all documents related to the study (e.g.

CELF assessment forms) rather than their own names. These codes will be used to label all data collected in the study.

The subject recruitment log and the consent/assent forms will be the only places where identifiable information is available. These will be stored securely as described above and separate from any data collected in the study.

Generating Unique Study ID Number:

The unique study ID number will be generated as follows: The first two digits will be the clinical site number (e.g. Bristol = 01, Hackney = 02, Newcastle = 03). The next two digits will describe the participant (e.g. child = 01, parent/carer = 02, SLT = 03). The final two digits will represent the order in which consent was received.

Example ID Code = 010101 (Bristol clinical site, child, first child consent form received).

Example ID Code = 020302 (Hackney clinical site, SLT, second clinician consent form received).

Language Explorer:

The data collection methodology for Language Explorer ensures the data collected is pseudonymised, using the child's study ID number. Although the Language Explorer app collects some information about the user, this is limited to ensure that identification is not possible. Specifically, when recording the age of the participant, only their Birth Month and Year are collected; when requesting the user's location, the user is only required to provide the first half of their Post Code.

Interview Data:

SLTs and parents/carers will be asked not to provide identifying information about themselves, their service, or any third parties during the interview. If any identifying information is provided, this will be made anonymous during transcription. The SLTs' and parent/carers' unique study ID number will be used in any written documentation. Recordings will be saved using the unique study ID number as the titles. The recordings will be securely stored on a password protected computer at BSLTRU, on the NBT server. Transcription of recordings will be undertaken by the RA/administrative clerk at the BSLTRU.

9.4 INDEMNITY

This is an NHS-sponsored research study. If an individual suffers negligent harm as a result of participating in the study, NHS indemnity covers NHS staff and those people responsible for conducting the trial who have honorary contracts with the relevant NHS Trust. In the case of non-negligent harm, the NHS is unable to agree in advance to pay compensation, but an *ex-gratia* payment may be considered in the event of a claim.

9.5 SPONSOR

North Bristol NHS Trust and Therapy Box will be adopting a co-sponsorship model.

NBT will monitor protocol compliance, safety and deviation reports where it relates to the conduct of the study (not the device). All deviations will be reported to MHRA.

Therapy Box will be responsible for the device and its function and design.

9.6 FUNDING

This study is funded by NIHR i4i programme (NIHR200889).

9.7 MONITORING

Monitoring is an integral role in the quality control of a research study and is designed to verify the quality of the study. According to ICH GCP (paragraph 5.18.1), the purpose of monitoring is to verify that:

- (a) The rights and well-being of the human subjects are protected;
- (b) The reported trial data are accurate, complete, and verifiable from source documents; and
- (c) The conduct of the trial is in compliance with the currently approved protocol/amendments, with GCP, and with the applicable regulatory requirements.

As the CI is an employee of NBT and NBT are sponsoring this pilot project, SOP RI/QMS/SOP/014 will be followed in relation to monitoring.

11. PUBLICATION POLICY

The research findings will be disseminated in the following manner:

- 1 Submitting abstracts for verbal and poster presentations at conferences such as RCSLT conference, DLD Clinical Excellence Networks
- 2 Submitting research papers to journals such as International Journal of Language and Communication Disorders, Child Language and Teaching Therapy,
- 3 Through the BSLTRU newsletter
- 4 Emailing the clinical teams of the three research sites (Bristol, Newcastle, Hackney) through their service leads.

13. APPENDICES

- Appendix A 'Protocol'
- Appendix B 'Recruitment Email (Clinicians)'
- Appendix C 'Participant Information Sheet (Clinicians)'
- Appendix D 'Consent Form (Clinicians)'
- Appendix E 'Email to Identifying Clinicians'
- Appendix F 'Cover Letter to Parents'
- Appendix G 'Participant Information Sheet (Parent)'
- Appendix H 'Consent Form (Parent)'
- Appendix I 'Consent Form (Child)'
- Appendix J 'Child Assent Form'
- Appendix K 'CELF-Preschool 2 UK Form'
- Appendix L 'CELF-5 UK Form'
- Appendix M 'Clinical Judgement Form'
- Appendix N 'Language Explorer Screenshots'
- Appendix O 'Interview Schedule (SLT)'
- Appendix P 'Interview Schedule (Parent)'
- Appendix Q 'Data Management Policy'
- Appendix R 'Participant Information Sheet (Child 6 to 7yrs)'
- Appendix S 'Participant Information Sheet (Child 4 to 5yrs);'
